7.2.3 Caregiver consent

Caregivers completing burden and quality of life assessments will be identified at the point of consent. Their eligibility will be checked (see section 6.3) and if suitable, they will be provided with a Caregiver Information Sheet and the opportunity to ask any questions. Those who wish to participate will be asked to sign a Caregiver Consent Form.

If consent is being given by a professional legal representative because a caregiver or other representative is not available, consent will only be obtained to approach a caregiver if and when a caregiver or other representative is identified.

Caregivers are free to withdraw from participating at any time for any reason. Unless the caregiver actively states that existing data may not be used, data will be used in accordance with the original signed Consent Form.

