10.3.3 Secondary outcome analysis

Secondary outcome measures will be analysed using the following methods:

- Mortality at 90 days will be analysed using Cox proportional hazards models.
- Any urgent or unplanned re-admission to 90 days and recurrent stroke or vascular events will be analysed using logistic regression.
- Home time, stroke-related health status, health and social care resource use and caregiver burden will be analysed using general linear models.
- EQ-5D-5L at 90 days will be compared between treatment groups using a general linear model adjusted for the baseline EQ-5D-5L.
- Length of stay will be analysed using a negative binomial model.

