10.8 Potential risk of missing or spurious data

The main analyses will use complete case data. Factors associated with availability of follow-up data will be assessed using logistic regression. Sensitivity analyses will include multiple imputation of missing outcome data.

Data will be gathered from the medical record by investigators. Missing data will be identified and queried by data management on a regular basis.

Participants and consented caregivers will provide their contact details at enrolment for the Day 90 follow-up. Outcome assessors will attempt to contact participants and caregivers to arrange a suitable time to complete the questionnaires. Where possible, data not obtained via telephone follow-up will be gathered from the participants' medical records.

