10.10 Economic evaluation

Economic evaluation will be performed by the Manchester Centre for Health Economics, University of Manchester. It will compare the cost and outcomes of standard care with standard care plus clarithromycin in PSP from the NHS/Personal Social Services perspective, using established quality criteria [38,39]. The impact of caregiver health and cost burden will also be explored [40].

Within-trial Cost-effectiveness Analysis – Will compare the difference in total health and social care cost and health outcomes for standard care with standard care plus clarithromycin over the study follow-up period (90 days).

Healthcare resource use per participant will be measured at baseline and at day 90 using routine data collection and a purposely designed healthcare services utilisation form (developed with the PPIE Group). Individual-level costs will be created by combining measured resource use with published unit costs. Costs will comprise:

- Secondary care (days spent on stroke unit, rehabilitation wards, general medical wards, intensive care unit, readmissions, Accident & Emergency, outpatient visits)
- Primary care (GP practice visits and phone contacts with the GP practice personnel)
- Time in care homes.

We will collect downstream health and social care costs and informal caregiver costs using an adapted Client Service Resource Inventory (CSRI) [41], combined with an adapted version of the Costs of Family Caregiving in Palliative Care(COFAC tool [42]). The COFAC tool has been shown to be valid, acceptable to caregivers and feasible to administer. The COFAC questionnaire seeks to capture data from a broad societal perspective which includes family caregiver costs. Health outcomes will be expressed as quality-adjusted life-years (QALYs). The EQ 5D-5L questionnaire will be administered to patients (or a proxy score from their caregivers) at baseline and at Day 90, so that QALYs can be calculated for each participant, using the area under the curve method. Following the NICE Reference Case, EQ-5D-5L responses will be converted to EQ-5D-3L utility values [43]. We will collect EQ-5D for caregivers and generate QALYs in the same way.

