Generalised linear model regression will estimate the total cost and total QALYs per arm controlling for baseline cost, baseline health utility, and other relevant participant characteristics. Bootstrapping will be used to handle stochastic uncertainty. The incremental cost-effectiveness ratio (ICER) will be calculated if either strategy is not dominated. Missing data will be handled using multiple imputation. Sensitivity analyses will investigate the robustness of the estimated ICER to different analysis assumptions.

Model-based Cost-effectiveness Analysis – Will compare the difference in cost and health outcomes for standard care with standard care plus clarithromycin over a lifetime time horizon (discount rate: 3.5%). A de novo cohort-level Markov model with an embedded decision tree will be developed to simulate the natural history of PSP and the impact of the intervention, with input from patients and clinicians.

Systematic reviews of existing cost effectiveness models in PSP, HAP, CAP and stroke will inform model structure. The Markov model health states will take into account level of disability from stroke using mRS scores [44]. Patient characteristics, transition probabilities, resource use and utilities associated with the two regimens will be taken from the trial population. Transition probabilities, resource use and utilities associated with stroke disease progression will be obtained from published evidence.

A probabilistic base case analysis will account for all input parameter uncertainty simultaneously. We will report total and incremental cost and QALYs, and ICER (if relevant). A cost-effectiveness threshold of £20-30,000 per QALY gained will be used to determine cost-effectiveness. A cost-effectiveness acceptability curve will report the probability of cost effectiveness and incremental net monetary benefit will be derived. Deterministic one-way sensitivity analyses will identify key drivers of cost-effectiveness. Potential scenario analyses include:

- 1. Alternative mapping methods to estimate EQ-5D-3L utility values from mRS
- 2. Inclusion of carer utility
- 3. Inclusion of carer costs.

Subgroup analysis will include stroke type, interval since admission, and whether the patient had received thrombolysis or thrombectomy.

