13.3 Patient and Public Involvement and Engagement

The PPIE lead for the CLASP study is a stroke survivor with several years of experience of both public engagement and PPIE in stroke. She has had key leadership roles in previous NIHR-funded studies (STOPtoolkit and CHOSEN) with appropriate support and mentoring. She has shared her lived experience of stroke to undergraduates at the University of Manchester, led on stroke public

engagement activities (e.g. Brain Health Day, Manchester 2023 https://stroke-impact.org/brain-healthday/) and works closely with regional stroke support groups.

During the trial design and funding application, partnership with The Stroke Association's Stroke Voices in Research (SViR) Group ensured that the trial design includes the priorities and views of stroke survivors. Prior to the Stage 1 Application, a PPIE workshop (Workshop 1) was co-developed to establish how stroke survivors and their caregivers would contribute to the proposal. In advance of the workshop, PPIE priorities for the trial design were identified. Workshop 1 comprised 4 stroke survivors and 1 family caregiver and took place online. The PPIE group confirmed the need for a clinical trial, in terms of importance of the unmet need and poor prognosis of patients with stroke-associated pneumonia (PSP). The intervention, where some participants would get extra antibiotics but all participants would still get usual antibiotic and other stroke unit care was felt to be justified. The panel were reassured that randomisation into the trial would not result in delays to patients care. In the workshop, the group considered participant eligibility and how to obtain consent. It was acknowledged that the majority of participants would have relatively severe stroke and many would lack capacity so personal or professional consultee consent would be appropriate in view of the poor prognosis of PSP. Finally, trial outcome measures were discussed. The group felt that the modified Rankin Scale (mRS) was the most appropriate outcome measure, because improving functional outcome rather than reducing mortality alone was considered important. Other outcomes, for example relating to caregiver burden and time spent at home were proposed.

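### As written, the day-90 EQ-5D-5L model would drop survivors who have a day-90 score but no baseline score

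*Protocol*

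**What the plan says.** For the quality-of-life outcome, protocol section 10.3.3 states: "EQ-5D-5L at 90 days will be compared between treatment groups using a general linear model adjusted for the baseline EQ-5D-5L". Section 10.8 sets the missing-data rule for the clinical analyses: "The main analyses will use complete case data". It then adds: "Sensitivity analyses will include multiple imputation of missing outcome data". It has no sentence on missing baseline covariates.

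Baseline EQ-5D-5L is on the list of baseline data in section 7.5. Section 10.10 says that the questionnaire is "administered to patients (or a proxy score from their caregivers) at baseline and at Day 90". On missing data, the same economic section says: "Missing data will be handled using multiple imputation". It does not limit this to outcomes.

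Two other places bear on whether a baseline score can be obtained. Section 13.3 records the view that "the majority of participants would have relatively severe stroke and many would lack capacity". Section 7.2.3 provides for a case that begins: "If consent is being given by a professional legal representative because a caregiver or other representative is not available".

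**The concern.** A general linear model needs a value for every covariate. With baseline EQ-5D-5L as a covariate and complete case as the rule, a participant whose day-90 score was obtained is removed when only the baseline score is absent. The stated sensitivity analysis does not bring that participant back, because the outcome is not what is missing.

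The protocol's own procedures make this pattern plausible. A participant without capacity depends on a caregiver for the baseline score, and enrolment with no caregiver at hand is foreseen. A caregiver may be found later (7.2.3) and capacity may return (7.2.1), so a day-90 score can exist where no baseline could be taken.

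At stake are the precision of a named secondary outcome and the population to which it applies. The people at risk of being left out are those without capacity and without a caregiver. Because section 10.10 allows imputation without that limit, the clinical and economic EQ-5D-5L results could also rest on different participants.

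**Working it through.** **The plan's own sample size first.** Section 10.1 gives 524 per group for 90% power at two-sided 5%, a common odds ratio of 0.7 and control mRS shares of 2:8:8:5:20:20:37.

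- Formula (Whitehead, proportional odds): n per arm = 6(z₀.₉₇₅ + z₀.₉₀)² / [(ln 0.7)² × (1 − Σp̄³)], where p̄ is the average of the two arms' shares.
- Shifting the control shares by 0.7 gives 2.8, 10.9, 10.2, 6.0, 22.0, 19.0 and 29.1%, so 1 − Σp̄³ is about 0.945.
- Result: 524.2 per arm, with power 89.99% at 524. Attrition: 524/0.9 rounds up to 583 per arm, 1166 in total. Both match the protocol.

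No sample size, power or missing-baseline rate is stated for EQ-5D-5L.

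**Survivors among 1048.**

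- No effect: 1048 × 0.63 = 660.
- Odds ratio 0.7: 524 × 0.63 = 330 control and 524 × 0.709 = 371 clarithromycin, 701 in total.

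**Loss if a share m of survivors has no baseline score.** The documents give neither m nor the baseline-outcome correlation ρ; both are assumptions. Observed outcomes lost = m × survivors, taking every survivor to have a day-90 score. The standard error is multiplied by 1/√(1 − m). The variance relative to an unadjusted analysis of all survivors is (1 − ρ²)/(1 − m).

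| m | Lost, no effect | Lost, OR 0.7 | SE factor | Variance ratio, ρ = 0.3 | Variance ratio, ρ = 0.5 |
|---|---|---|---|---|---|
| 10% | 66 | 70 | 1.05 | 1.01 | 0.83 |
| 20% | 132 | 140 | 1.12 | 1.14 | 0.94 |
| 30% | 198 | 210 | 1.20 | 1.30 | 1.07 |
| 40% | 264 | 281 | 1.29 | 1.52 | 1.25 |

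The ratio is below 1 only if m < ρ². So complete-case adjustment is more precise than no adjustment only when the missing share is below 9% at ρ = 0.3 or 25% at ρ = 0.5.

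**Power**, at an assumed standardised difference of 0.25, ρ = 0.3 and 701 survivors: 91, 87, 83 and 77% for complete case at m = 10, 20, 30 and 40%. It is about 93% if everyone is kept with a filled baseline, and 91% unadjusted.

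**Simulation** (1500 runs, 680 participants, 23% missing a baseline, more often the sicker ones):

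- With a constant true effect of 0.20, complete case averages 0.202 with SD 0.081. A missing-indicator analysis averages 0.200 with SD 0.072. The unadjusted analysis has SD 0.077.
- If the effect varies with baseline, complete case averages 0.233 against about 0.20 in all survivors. It then answers the question for a healthier group.

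**The case against.** The strongest reply is that this belongs in the statistical analysis plan. Sections 10.3 and 10.9 promise detailed plans approved before unblinding, and handling of missing covariates is commonly left to them. Section 10.8 says that sensitivity analyses will include imputation, so its list is open, and complete case could be read as complete outcome data. This stands in part: the protocol does not say in terms that these participants are discarded. But it has already fixed the covariate, the complete-case rule and what is imputed. On the plain reading those choices drop the participant, and a later plan would have to reinterpret them.

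The second reply is that the loss may be small. Baseline EQ-5D-5L is listed for all participants, a caregiver proxy is allowed, and a relative may be reached by telephone for consent (7.2.1). This stands. A reader might infer that everyone enrolled through a professional representative has no baseline score. The documents do not say so: section 7.2.3 concerns the caregivers' own assessments and shows only that a caregiver may be unavailable at consent. People without a baseline may also be more likely to die or to lack a day-90 score, so the counts above are upper figures for each assumed share.

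A reader might also apply the clarithromycin arm's 71% survival to all 1048 and reach 744 survivors. Allocation is 1:1 and 37% of controls are assumed to die, so 701 is the coherent figure at an odds ratio of 0.7.

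**Conclusion.** The point holds in conditional form: a survivor with an observed day-90 EQ-5D-5L would be dropped if the baseline score is missing, and the named sensitivity analysis would not cover that case. The cost is at most about 66 to 70 observed outcomes for each 10% of survivors without a baseline, with the standard error up about 5% at 10% missing and 29% at 40%. The missing share and the correlation are assumptions, and the true loss could be small.

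It is tempting to conclude that the comparison between arms is biased. The documents do not support that. If baseline is recorded before allocation, its absence cannot depend on arm, and the simulation with a constant effect showed no bias. What remains is lost precision and a narrower analysed population, for one secondary outcome. The primary analysis and the sample size are untouched.

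**What to change.** State in sections 10.3.3 and 10.8 that participants with an observed day-90 EQ-5D-5L are not excluded for a missing baseline EQ-5D-5L. Fill the missing baseline with the overall mean across both arms and add a missing-baseline indicator, or include the baseline in the multiple imputation. Report the number with a missing baseline by arm.

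Keep the rule to this covariate. Section 10.5 otherwise adjusts only for the minimisation variables. Mean-filling subgroup factors in section 10.4, such as CRP or NEWS-2, would place participants in a subgroup artificially.

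The cost is one sentence and a few lines of analysis code. It can be settled before any unblinded data are seen.

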10.4 Subgroup analyses

Subgroup analyses are planned in relation to:

- Age (<80 v ≥80 years)
- Sex (male v female)
- Baseline NIHSS (<12 v ≥12)
- Pre-morbid mRS (0-1 v 2-3 v 4-5)
- Ethnicity (white v non-white)
- Stroke type (ischaemic stroke v ICH)
- Interval since admission (<72 v 73-168 v 169-336 hours)
- Received thrombolysis (yes v no)
- Received thrombectomy (yes v no)
- Highest recorded CRP concentration prior to starting antibiotics (<75 v ≥75 mg/l)
- Highest recorded NEWS-2 score prior to starting antibiotics (dichotomised at median)

Differences in treatment effects between subgroups will be assessed by extending the primary analysis regression model to include treatment-by-subgroup interactions. Within-subgroup treatment effects estimates will be reported with 95% CIs, interaction p-values will be reported, and results will be presented with a forest plot.

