2 RATIONALE

Antibiotics are the mainstay of treatment for PSP, however there is a lack of evidence to guide treatment compared to other types of pneumonia as identified in our recent systematic review [17], for example CAP [18]. The effectiveness of different antibiotic classes and the importance of potential immunomodulatory effect of some drug classes in PSP remains uncertain. This trial is a pragmatic randomised trial of immunomodulatory macrolide antibiotic therapy added to usual, non-macrolide antibiotic treatment for PSP, which could improve clinical outcomes for patients and their families and provide health economic benefits. Our results will directly inform national stroke treatment guidelines and clinical practice.

Macrolide antibiotics have powerful immunomodulatory properties and have been shown to reduce exacerbations in people with chronic obstructive pulmonary disease (COPD) and to improve lung function in people with cystic fibrosis [19]. Given the clear role of inflammation in PSP, macrolides are logical agents to assess to see whether their antimicrobial and immunomodulatory effects improve the poor outcomes in PSP. Whilst there may be differences in immunomodulatory effects between macrolide drugs, immunomodulation is generally accepted to be a class effect [20]. There is no

consistent difference in side effect profile between different macrolides [21]. Of the newer macrolides, clarithromycin and azithromycin are available as oral or intravenous (IV) formulations. In our recent survey of UK stroke units, IV and oral clarithromycin were available in 93% of responding units, whereas IV azithromycin was only available in 45% of units. This is important as the majority of patients with PSP have dysphagia and require IV antibiotics, at least until a consistent oral or enteral route is established. We have therefore chosen clarithromycin for this trial. We have opted for 5 days treatment with clarithromycin to align with current antibiotic recommendations for pneumonia and to reduce the risks of antimicrobial resistance [18,22]. Given their poor outcome, the presence of a usually severe stroke and possible dysphagia, participants would be considered seriously ill and requiring initial intravenous therapy (dose 500 mg twice daily). As soon as a reliable oral or enteral route is established, participants should switch to oral/enteral dosing at the dose for severe respiratory infection (500mg twice daily) in line with usual IVOS policies.

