10 STATISTICS AND DATA ANALYSIS

10.1 Sample size calculation

In our preliminary study of antibiotic classes [36] based on observational data we reported a common Odds Ratio (OR) of approximately 0.5 for those receiving macrolides. This observation was not a pre-specified hypothesis. We have applied the 'rule of thumb' to target an effect size that is half that observed in such circumstances. Working on the log OR scale, half the effect size can be back-transformed to our target OR of 0.7.

A sample size of 524 participants per group would give 90% power at a two-sided 5% significance level to detect a common OR of 0.7. This is based on analysis by ordinal logistic regression of the mRS at 90 days, assuming the distribution of 90 day mRS in the control arm to be 2:8:8:5:20:20:37 across mRS 0-6. We propose an adaptive (group sequential) design, with an interim analysis after 50% have provided primary outcome data. If the interim analysis z-statistic for the treatment effect is less than -3.09 (i.e. is in favour of clarithromycin at a one-sided p<0.001), then we shall stop the trial for efficacy. If the interim analysis statistic is greater than -0.5, we shall stop for futility. Otherwise, we shall complete the trial as planned, without adjustment of the final analysis p-value.

Simulations of this approach under alternative assumptions regarding the true common OR (N=10,000 simulated trials at ORs from 0.5 to 1.0) suggest that there is minimal loss of power, and no inflation of the Type I error rate (see Table 3 below). Under the null hypothesis of no treatment effect, the one-sided probability of a false positive result is 0.025, slightly lower than running the full trial (0.026), and there is a 69% probability that the trial will stop early for futility, leading to an expected total sample size of 685. If the true OR is equal to 0.7 (the target value

Version 1.0 – 12 December 2024

CLASP

for the sample size calculation), the power of the adaptive design is 88.3%, close to that achieved by running the full trial (89.8%), but with 25.5% chance of trial stopping early (21.7% for efficacy, 3.8% for futility), the expected sample size is 914. Should the true common OR be 0.5 (as observed in observational studies), the adaptive approach gave a positive result in all simulated trials, with 91.7% stopping early, leading to an expected sample size of 568 (Table 3).

| | Standard Approach | | Adaptive Approach | | | |

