10.3.2 Primary outcome analysis

The primary efficacy analysis will estimate the average treatment effect in those randomised to receive clarithromycin, according to the intention to treat principle.

Ordinal logistic regression will be used to analyse the primary outcome (mRS at 90 days). ORs, corresponding 95% confidence intervals and p-values will be reported.

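### Section 10.4 tests effect modification by CRP and NEWS-2 only between two groups, which loses power for the interaction if the treatment effect changes gradually along the scale

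*Protocol*

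**What the plan says.** Section 10.4 of the protocol lists eleven subgroup variables. The last two are "Highest recorded CRP concentration prior to starting antibiotics (<75 v ≥75 mg/l" and "Highest recorded NEWS-2 score prior to starting antibiotics (dichotomised at median". The method is the same for all eleven: "Differences in treatment effects between subgroups will be assessed by extending the primary analysis regression model to include treatment-by-subgroup interactions". Within-subgroup estimates with 95% confidence intervals, interaction p-values and a forest plot are to be reported. No interaction with a continuous variable is mentioned.

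The model being extended is the one in section 10.3.2: "Ordinal logistic regression will be used to analyse the primary outcome (mRS at 90 days". Section 7.5 collects baseline CRP (mg/L) and NEWS-2 as the highest values in the 72 hours before randomisation. The protocol gives no reason for the 75 mg/l cut, no expected distribution for either variable and no power for any interaction.

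Section 2 gives the reason for looking at inflammation: "Given the clear role of inflammation in PSP, macrolides are logical agents to assess".

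**The concern.** The trial adds an antibiotic class chosen partly for its immunomodulatory action. It is natural to ask whether the effect on 90-day mRS varies with how inflamed or how ill the patient is, and CRP and NEWS-2 are the only variables in section 10.4 that address this.

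A two-group interaction test ignores all variation within each group. A CRP of 74 and one of 76 mg/l fall on opposite sides, while 80 and 300 mg/l count as the same. For NEWS-2 the cut is known only once the trial's own data are in, and because the score is an integer, ties at the median will make the groups uneven.

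Interaction tests have little power to spare. If the effect changes gradually, the two-group test is more likely to miss the gradient than a test that uses the recorded values.

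**Working it through.** **Inputs from the protocol.** Section 10.1: 524 per group, 90% power, two-sided 5%, common OR 0.7, control-arm mRS distribution 2:8:8:5:20:20:37. Section 10.4: the two cuts and the interaction method.

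**Inputs assumed.** The distribution of CRP and NEWS-2, the position of the CRP cut within it, and the shape of the interaction. The protocol gives none of these.

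**1. Reproduce the protocol's own figure.** Whitehead's formula for proportional odds is N = 12(z₀.₉₇₅ + z₀.₉₀)² / [(ln OR)²(1 − Σp̄³)], where p̄ is the mean of the two arms' category probabilities. With OR 0.7 it gives N = 1048.3, or 524.2 per arm, and power 0.900 at N = 1048. The stated 524 per group reproduces, so the model and mRS distribution are a sound base for the next steps.

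**2. Information kept by a split.** For a linear interaction, the efficiency of a two-group split relative to the continuous moderator is the squared correlation between the value and the group indicator. For a normal moderator with a proportion p on one side of the cut, this is φ(z_p)² / [p(1 − p)].

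| Split | Efficiency | Loss |
|---|---|---|
| 50:50 | 0.637 | 36% |
| 60:40 | 0.622 | 38% |
| 65:35 | 0.603 | 40% |
| 70:30 | 0.576 | 42% |
| 80:20 | 0.490 | 51% |

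**3. What this means for power.** An interaction with 80% power on the continuous value has a mean z of 1.96 + 0.84 = 2.80.
- 50:50 split: 2.80 × √0.637 = 2.24, power about 61%.
- 70:30 split: 2.80 × √0.576 = 2.13, power about 57%.
- If continuous power is only 50%, the split versions have about 35% and 32%.

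**4. Check by simulation.** Proportional-odds model, N = 1048, the protocol's mRS distribution, OR 0.7 at the mean of the moderator, interaction −0.30 and prognostic effect 0.3 log-odds per SD, 600 trials per split.

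| Lower : upper group | Efficiency | Power, continuous | Power, split |
|---|---|---|---|
| 50 : 50 | 0.66 | 75% | 59% |
| 30 : 70 | 0.59 | 77% | 54% |
| 70 : 30 | 0.55 | 77% | 48% |

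The losses are about 34%, 41% and 45%, in line with step 2.

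A second simulation (1,000 trials per scenario, prognostic effect 0.4 per SD) varied the gradient. With the OR running from 1.0 at −1 SD to 0.5 at +1 SD, power was 89% continuous, 68% at a median split and 65% at 30:70. With 0.9 to 0.55 it was 59%, 40% and 35–37%. Type I error was 5.5–5.7% for every version.

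**5. Sensitivity to the assumed distribution.**
- Uniform moderator cut at its median: 25% loss.
- Integer NEWS-2 with assumed mean 3–6 and SD 2–3: 33–36%.
- Log-normal CRP with assumed median 50–120 mg/l and an interaction linear in log CRP: 36–44%.
- The same CRP distributions with an interaction linear in raw CRP: 50% or more.
- A true step in the effect exactly at the cut: no loss.

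**The case against.** Pre-specified groups with interaction p-values, confidence intervals and a forest plot are conventional and easy to read. The cuts are applied to baseline variables, cause no bias and do not inflate the Type I error. These are two of eleven subsidiary analyses, and no decision rule depends on them. A final SAP is still to be approved before database lock and could add a continuous term. With the gentler gradient even the continuous test has only 59% power, so a null result would be weak evidence either way. All of this stands, and it limits the weight of the point. It does not make the two-group test the better choice, because section 10.4 states the grouped method and a SAP that follows it carries the loss forward.

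A further objection is that section 10.4 refers to values before antibiotics start, whereas section 7.5 collects the highest value in the 72 hours before randomisation, which may come up to 24 hours after the first dose (section 6.1). The definitions do differ, but the difference affects split and continuous versions equally.

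Three stronger readings are tempting and are not supported:
- A reader might infer that these subgroups are the plan's only tests of its inflammation rationale. Section 3.3.3 also lists highest CRP, white cell count and temperature over the first 7 days as exploratory outcomes. NEWS-2 is itself a general physiological score.
- A reader might take a larger benefit at higher CRP to be a prediction of the trial, or expect a missed gradient to misdirect guidelines. The protocol says neither.
- A reader might take 36–42% as a property of this trial, or as participants discarded. It is a loss of information on one interaction term under stated assumptions. Nor is CRP necessarily cut into halves, since the position of 75 mg/l in this population is unknown.

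**Conclusion.** The point holds as a cheap improvement. Section 10.4 assesses effect modification by CRP and NEWS-2, its only listed effect modifiers reflecting inflammation or severity of infection, solely between two groups. That costs power for the interaction test when the effect changes gradually.

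The 36% (50:50) and 42% (70:30) figures assume a moderator that is normal on the scale used and a linear gradient. The wider range of about 25% to over 50%, with zero for a threshold exactly at the cut, is the honest statement of size. The power figures at N = 1048 also assume that the trial runs to its full size. If it stops at the interim analysis of 524 participants, information on the interaction is roughly halved for either method.

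The primary analysis, the sample size and the Type I error are unaffected.

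**What to change.** In section 10.4, and then in the final SAP, state that the interaction p-value for CRP (log scale) and for NEWS-2 comes from the treatment-by-continuous-value term in the primary ordinal model, with a spline check of linearity. Keep the <75 v ≥75 mg/l and median groups for the within-subgroup estimates and the forest plot.

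The same can be done for interval since admission, in hours. This would also remove the small gap in its present groups, where exactly 72 hours falls in none.

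The cost is wording, to be settled before treatment allocations are unblinded. No new data are needed and every planned display is kept. The downside is that the main interaction term assumes a roughly linear gradient. The spline checks that assumption, and a sharp threshold at the cut would be better detected by the groups.
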